2.6.2.4 Change from baseline in SF-BPI score (pain severity and pain interference)

Participant reported secondary endpoints are the mean change from baseline in Short-Form Brief Pain Inventory (SF-BPI) at Day 360 in pain severity and pain interference score.

The null hypothesis to be rejected for the relevant secondary endpoints are:

- H_{05} : The mean change from baseline in SF-BPI pain severity score to Day 360 is equal between treatment groups.
- H_{06} : The mean change from baseline in SF-BPI pain interference score to Day 360 is equal between treatment groups.

The SF-BPI is a self-administered standardized fifteen items questionnaire that assesses how pain interferes with or influences a participant's life. The query period covers the past 24 hours and takes 5 minutes for the participant to complete (see also Section 8.5.1.1 in Protocol).

The pain severity and interference scores will be derived for each visit between screening and EOT/EOS (Day 360). To derive the pain severity score the average of the four items concerning pain intensity will be taken. Accordingly, the pain interference score will be calculated as the average of the seven items concerning pain interference. Both scores will be between 1 and 10. The remaining items do not contribute to the scoring. An overall score is not defined.

If there is missing data for a participant and the available data is more than 50% for the corresponding domain (3 of 4 [pain severity] or 4 of 7 [pain interference], respectively), the missing items will be imputed using the mean score of the non-missing item scores. Else no imputation will be done and the domain score will be imputed according to the general handling of missing values as described in [Section 2.6.4](#).

The higher the scores, the poorer is the condition of the participant. Changes from baseline scores are defined as clinically relevant, if the pain severity score and the pain intensity score change by at least 2 points.

The absolute change from baseline in SF-BPI pain severity score and SF-BPI pain interference score will be analyzed using a mixed model for repeated measures (MMRM) including

treatment group, CV risk category, scheduled visit and the interaction of treatment group with scheduled visit as factors and corresponding baseline SF-BPI score and the interaction of corresponding baseline SF-BPI score with scheduled visit as covariates. To allow adjustment for correlations between time points within participants, an unstructured variance-covariance structure will be used.

The null hypothesis of equal mean changes between both groups at day 360 visits will be tested by an appropriate linear contrast of the variable treatment and treatment by visit interaction. The adjusted mean change from baseline as well as the treatment difference and their corresponding 95% confidence intervals will be presented.

Least square means of each treatment group and estimated treatment differences at visits and corresponding 95% confidence intervals will be presented graphically.

Additionally, the odds ratio between inclisiran vs. placebo of the participants achieving a clinically relevant change in pain severity score and pain intensity score from baseline to Day 360 will be estimated using a logistic regression model. Treatment and CV risk category will be included as factors in the model. The odds ratio and its 95% confidence interval (CI) and p-value will be estimated.

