8.5.1.1 Short-Form Brief Pain Inventory (SF-BPI)

The SF-BPI is a self-administered standardized fifteen items questionnaire that assesses how pain interferes with or influences a participant's life. The query period covers the past 24 hours and takes 5 minutes for the participant to complete. The first item is a screening question about the participant's pain on the day. The questionnaire is then composed of pain drawing diagrams, four items about pain intensity (worst pain, least pain, average pain, pain right now), two items on pain relief treatment or medication, and one item on pain interference, with seven sub-items (general activity, mood, walking ability, normal walk, relations with other people, sleep, and enjoyment of life). The SF-BPI includes two main scores: a pain severity score and a pain interference score. The pain severity score combines the information of the four items about pain intensity, which are rated from 0, no pain, to 10, pain as bad as you can imagine. To derive the pain severity score the average of the four items will be taken. The pain interference is calculated similarly using the seven items regarding pain interference, which are rated from 0, does not interfere, to 10, completely interferes. The pain interference score will be the average of these seven items. Both scores will be between 0 and 10. The remaining items of the questionnaire do not contribute to the scoring. Higher scores correspond to a poorer condition of the participant. The first item, pain drawing diagrams (painful and most painful areas) and the items on pain relief treatment or medication (list of the treatments and amount of relief) do not contribute to the scoring. It has been validated ([Tan et al 2005](#), [Keller et al 2004](#)) for use with non-malignant pain populations and has been used in statin trials ([Cleeland 2009](#)).

The SF-BPI will be recorded as outlined in the Assessment Schedule ([Table 8-1](#)).

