The overall study duration will be at least 360 days but can be longer depending on individual screening and run-in period time.

Around 1760 participants who meet the eligibility criteria will be randomized 1:1 at baseline. Since 35% of participants are expected to be screening or run-in failures, approximately 2700 participants are anticipated to be screened.

No interim analysis is planned for this study.

Figure 1-1 Study design

¹ Duration of the Statin Titration period during the run-in can be shorter than the depicted 120 days (see Protocol section 3.2)

² Duration of the Rosuvastatin Titration period during the double-blind treatment period can be shorter or longer (broken line arrow) than the depicted 90 days in both treatment arms (see Protocol section 3.4)

Notes: All days in parenthesis represent optional visits. A mandatory safety follow-up phone call must be given at Day 390.

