2.1.1.5 Baseline

Baseline value is defined as the last non-missing value prior to the start of the treatment period, which means prior to the first injection of the blinded investigational treatment. If the date of assessment is the same as date of first injection but time is not available for comparison, the assessment is assumed to be prior to the administration of blinded investigational treatment. Questionnaires assessments at Day 1 are considered as baseline irrespective of time collected. Participants pain diary is not collected prior to first injection of the blinded investigational treatment, therefore baseline is not defined for the same.

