2.6.2.5 Control of Familywise type I error rate

1-sided p-values and alpha level of 0.025 are considered for the testing procedure.

[figure not shown]
Hypotheses are grouped into three families. The first family contains the primary hypothesis H_{01} . The second family contains two secondary hypotheses H_{02} and H_{03} . The third family contains the remaining secondary hypotheses H_{04} , H_{05} and H_{06} . A hierarchical testing strategy is applied to these three families to control the familywise type I error rate in the strong sense. First H_{01} is tested at level α . If it is rejected, we test the second family using a closed test at level α . If both hypotheses are rejected, we test the third family using the Hommel procedure at level α . When not all hypotheses in a family can be rejected, testing stops at the corresponding family and does not proceed to test the next family.

Within the second family, a closed test procedure based on weighted Simes tests is applied with 80% weight for H_{02} and 20% weight for H_{03} . First the two nominal p-values for the two hypotheses are simultaneously compared to α . If both nominal p-values are less or equal α , the two null hypotheses are rejected. Otherwise the individual nominal p-values will be compared to the pre-specified weighted alpha. If the p-value for H_{02} is less or equal 0.8α , H_{02} is rejected; if the p-value for H_{03} is less or equal 0.2α , H_{03} is rejected.

Within the third family, the Hommel procedure is applied. Let the ordered p-values for H_{04} , H_{05} and H_{06} be $p(1) \leq p(2) \leq p(3)$ and the corresponding hypotheses $H(1)$, $H(2)$ and $H(3)$. First if $p(3)$ is less or equal α , we can reject all three hypotheses. Otherwise, if $p(2)$ is less or equal $\alpha/2$, we can reject $H(2)$ and $H(1)$. Otherwise, if $p(1) \leq \alpha/3$ or ($p(1) \leq \alpha/2$ and $p(2) \leq 2\alpha/3$), $H(1)$ is rejected.

For more details see also [Figure 2-2](#).

Figure 2-2 Applied testing procedure

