3.1 Primary endpoint(s)

The assumption for the occurrence of LDL-C target attainment on day 90 in the inclisiran-arm is based on the ORION study data set. In CCI of participants achieved an LDL-C level CCI mg/dL target at day 90 CCI (Ray et al., 2020). In CCI of participants achieved an LDL-C level CCI mg/dL at day 90 CCI (Ray et al., 2020). Assuming CCI, approx. CCI of participants achieve their individual LDL-C target at day 90. For the assumption of LDL-C target attainment at day 90 in the placebo arm, the EXPLORER trial reports response rates for CCI (Ballantyne et al., 2007): CCI of participants achieved an LDL-C level CCI mg/dL at day CCI. Mean LDL-C level at day CCI was CCI, so it can be estimated that approx. CCI of participants may have reached the CCI target. Based on the study population and treatment regime herein, day CCI of EXPLORER trial likely relates to day 90 of the present study. With the above stated assumption of a CCI among the participant population, CCI of participants are considered to reach their LDL-C target at day 90. Considering the high LDL-C levels at baseline in the EXPLORER trial compared to ORION trials, herein, a slightly higher goal attainment rate of approx. CCI at day 90 for participants in the comparator arm is assumed. Under these assumptions, CCI participants per arm are required based on a chi-squared test of proportions to achieve 90% power on a two-sided, 5% significance level. In order to compensate for missing values and other protocol deviations, approximately 880 participants per arm (approximately 1760 participants in total) should be enrolled/randomized into this trial.

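### The confirmatory SF-BPI models (H05, H06) omit the screening SF-BPI score as a covariate; the planned test is valid, but a modest and unquantified gain in precision is left unused

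*SAP*

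**What the plan says.** Protocol Table 8-1 schedules the SF-BPI at screening and on Day 1, with none at the run-in visits or Day -10. Protocol 8.5.1.1 gives the recall period: "The query period covers the past 24 hours and takes 5 minutes for the participant to complete". SAP 2.6.2.4 states: "The pain severity and interference scores will be derived for each visit between screening and EOT/EOS (Day 360", so the screening score is computed in any case.

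SAP 2.1.1.5 fixes which score is baseline. The general rule is "Baseline value is defined as the last non-missing value prior to the start of the treatment period", and for questionnaires "Questionnaires assessments at Day 1 are considered as baseline irrespective of time collected". Day 1 is therefore the baseline. By the general rule, the screening score could stand in when Day 1 is missing.

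The mixed model for repeated measures (MMRM) for H05 and H06 has treatment, CV risk category, visit and treatment-by-visit, with "corresponding baseline SF-BPI score and the interaction of corresponding baseline SF-BPI score with scheduled visit as covariates". SAP 5.5.2.1 and Protocol 12.5.2.4 give the same model. SAP 5.5.3 imputes a missing baseline from treatment and CV risk category alone and then works forward visit by visit. No published SF-BPI model or imputation step uses screening as a separate variable.

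**The concern.** One 24-hour pain score is a noisy reading of a participant's usual pain. A second reading of the same domain, also taken before randomization, can sharpen the adjustment. For participants already on their maximum tolerated statin dose, the two readings are at most about 14 days apart (Protocol 8.1) on a stable statin, so they come close to replicates.

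H05 and H06 are confirmatory and sit in the last family of the hierarchy. Neither document states a power for them: the sample size sections cover target attainment and muscle-related adverse events only. Within that family, the Hommel procedure applies thresholds of alpha/2 or alpha/3 when the largest p-value exceeds alpha, so the width of the Day 360 contrast matters. What is at stake is precision. The endpoint, the baseline definition and the estimand would all stay as they are.

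**Working it through.** **No figure to reproduce.** The documents give no SD, effect size, correlation or power for the SF-BPI.

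**Inputs from the documents**
- Significance level (SAP 2.6.2.5): "1-sided p-values and alpha level of 0.025 are considered for the testing procedure". The critical value is 1.96.
- Sample size (SAP 3.1): "approximately 880 participants per arm (approximately 1760 participants in total) should be enrolled/randomized into this trial". This was set on the primary endpoint.
- Post-baseline SF-BPI visits (SAP Table 2-1): Days 30, 60, 90, 150, 210, 270, 330 and 360, which is eight.
- Longest gap from screening to Day 1 (Protocol Section 3): 14 + 120 + 10 = 144 days.

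**Assumed:** the three correlations rb = corr(Day 1, Day 360), rs = corr(screening, Day 360) and rsb = corr(screening, Day 1), and a power of 80% under the planned model as an anchor.

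**Method.** With complete data and covariate-by-visit terms, the unstructured MMRM behaves at Day 360 essentially like an ANCOVA. Per unit variance, the residual variance is:
- Day 1 only: V1 = 1 − rb²
- Day 1 and screening: V2 = 1 − (rb² + rs² − 2·rb·rs·rsb)/(1 − rsb²)

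With R = V2/V1, the gain in effective sample size is 1/R − 1. The anchored power is Φ(2.80/√R − 1.96), where 2.80 = 1.96 + 0.84.

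**Worked example** (all three at 0.5): V1 = 1 − 0.25 = 0.750. V2 = 1 − (0.25 + 0.25 − 0.25)/0.75 = 0.667. R = 0.889, so the gain is 12.5%. That is equivalent to 880/0.889 ≈ 990 per arm. Power is Φ(2.97 − 1.96) = 84.4%.

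| rb / rs / rsb | V1 → V2 | Gain | 80% power becomes |
|---|---|---|---|
| 0.7 / 0.7 / 0.7 | 0.510 → 0.424 | 20% | 86.7% |
| 0.6 / 0.6 / 0.6 | 0.640 → 0.550 | 16% | 85.6% |
| 0.5 / 0.5 / 0.5 | 0.750 → 0.667 | 12% | 84.4% |
| 0.6 / 0.6 / 0.7 | 0.640 → 0.576 | 11% | 83.9% |
| 0.5 / 0.5 / 0.6 | 0.750 → 0.688 | 9% | 83.3% |
| 0.6 / 0.6 / 0.8 | 0.640 → 0.600 | 7% | 82.5% |
| 0.5 / 0.5 / 0.7 | 0.750 → 0.706 | 6% | 82.3% |
| 0.5 / 0.45 / 0.6 | 0.750 → 0.715 | 5% | 81.9% |
| 0.5 / 0.45 / 0.7 | 0.750 → 0.730 | 3% | 81.0% |
| 0.6 / 0.5 / 0.7 | 0.640 → 0.627 | 2% | 80.8% |
| 0.5 / 0.4 / 0.6 | 0.750 → 0.734 | 2% | 80.8% |
| 0.5 / 0.4 / 0.7 | 0.750 → 0.745 | 0.7% | 80.3% |
| 0.5 / 0.35 / 0.7 | 0.750 → 0.750 | 0 | 80.0% |

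The last row is the case rs = rb × rsb (0.5 × 0.7 = 0.35), where screening carries nothing beyond Day 1. The 9% and 11% rows need rsb to exceed rb by only 0.1, with screening as predictive of Day 360 as Day 1 is.

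**Simulation check.** In 3,000 simulated trials of 880 per arm with normal scores, the variance ratio was 0.90 at equal correlations of 0.5 (formula 0.889) and 0.86 at 0.6 (formula 0.859).

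**Cost in parameters.** One screening term plus its interaction with eight visits adds 1 + 7 = 8 parameters per model.

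**The case against.** The planned model is conventional and valid and matches the protocol. How many pre-randomization scores to adjust for is partly a matter of preference. That stands: a reader might infer from the omission that the test is biased or that its error rate is off, and nothing in the documents supports that.

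A reader might also take 12–20% as the expected gain. Those figures need scores days to weeks apart to correlate no better than scores about a year apart. Repeat scores usually correlate more when closer in time, and the gain then drops, mostly to single digits and possibly to zero. This objection also stands.

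Screening is not a uniform second baseline. After run-in it can be more than four months old and precede statin up-titration, so it probably adds less there. The proportion entering run-in is not given.

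The benefit is conditional as well. H05 and H06 are tested only if H01, H02 and H03 are all rejected, and the power figures above ignore both that gate and Hommel.

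Finally, the change is more than one line of text, and nothing in the documents shows that missing screening scores will be few. What survives the objections is that the covariate is fixed before randomization, is already collected and scored, introduces no bias, and cannot materially reduce precision at this sample size.

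**Conclusion.** The point holds as an efficiency gap. Two pre-randomization scores exist for each domain. One is used as a covariate, and the other is scored and then left out of both the models and the imputation.

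The size is unknown because the documents give no SF-BPI correlations. The assumed values give a range from zero to about 20%. Most cases with screening and Day 1 as the closer pair fall at about 2–7%, and they reach 9–11% only under the mildest such departure from equality. At an assumed 80% power, 2–7% is worth roughly one to two and a half percentage points for a single test.

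It would be too strong to say that precision is lost for nothing, or that the models adjust for Day 1 alone. CV risk category is also in the model, screening may already replace a missing Day 1 score, and the zero-gain case cannot be excluded. Zero gain does seem unlikely when Day 1 is itself a noisy 24-hour reading.

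**What to change.** Before unblinding:

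1. Keep Day 1 as the baseline for the change score.
2. In SAP 2.6.2.4 and 5.5.2.1, add the same-domain screening score and its interaction with scheduled visit as covariates in both MMRMs.
3. In SAP 5.5.3, add the screening score to the SF-BPI imputation, including the jump-to-reference step. Use it to impute missing baselines, and impute missing screening scores too.
4. State that a missing Day 1 SF-BPI score is imputed using screening and not replaced by it. Otherwise the two covariates would be identical for those participants.
5. Record the departure from Protocol 12.5.2.4 in SAP Section 4, which already lists such changes.

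The cost is about eight extra parameters per model among about 1760 participants, plus minor SAP and programming edits in several places. No new data are needed.

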2.6 Analysis supporting secondary objectives

2.6.1 Secondary endpoint(s)

The population and the treatment of interest associated with the secondary estimand are the same as for the primary estimand (see [Section 1.2.1](#)).

The secondary estimands are defined by the evaluation of treatment effect on the following endpoints and summary measures in [Table 2-3](#):

Table 2-3 Endpoints and summary measures of the secondary estimand

Endpoint	Summary Measure
Relative change (percentage change) from baseline to mean LDL-C level over the double-blind study period (averaged over all post baseline visits)	Difference in mean relative change
Proportion of participants experiencing at least one muscle-related AE as defined in the SMQ rhabdomyolysis / myopathy from Day 1 to Day 360	OR (odds ratio)
Annualized number of days participants experiencing self-reported pain from Day 1 to Day 360	Annualized RR (rate ratio)
Change from baseline in SF-BPI pain severity score at Day 360	Difference in mean relative change
Change from baseline in SF-BPI pain interference score at Day 360	Difference in mean relative change
Proportion of participants with clinically relevant change in SF-BPI pain severity score from baseline to Day 360.	OR (odds ratio)
Proportion of participants with clinically relevant change in SF-BPI pain interference score from Baseline to Day 360.	OR (odds ratio)

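### The SF-BPI responder rule gives no direction and misnames the interference score, so its odds ratio cannot be read as benefit or harm

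*SAP*

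**What the plan says.** Protocol Table 2-1 and SAP Tables 1-1 and 2-3 list two SF-BPI responder endpoints at Day 360, one for pain severity and one for pain interference. Table 2-3 gives each an odds ratio as its summary measure.

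The only visible definition is in SAP 2.6.2.4, where a change is "clinically relevant, if the pain severity score and the pain intensity score change by at least 2 points". The sentence before it states that "The higher the scores, the poorer is the condition of the participant", but the rule does not use this. The analysis is a logistic regression, with treatment and CV risk category as factors, of participants "achieving a clinically relevant change in pain severity score and pain intensity score from baseline to Day 360". An odds ratio, 95% CI and p-value are planned.

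Two labels in the same part of the SAP also disagree with other text:

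- Table 2-3 gives "Difference in mean relative change" as the summary measure for both SF-BPI mean-change endpoints, while SAP 2.6.2.4 says "The absolute change from baseline in SF-BPI pain severity score and SF-BPI pain interference score will be analyzed" with a mixed model for repeated measures (MMRM).
- SAP 2.6.2.4 says "Both scores will be between 1 and 10", while Protocol 8.5.1.1 says "Both scores will be between 0 and 10".

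**The concern.** The secondary objective is superiority of inclisiran on pain-related quality of life. A responder analysis serves it only if the event is good or bad for the participant. Here the event is a change of 2 points or more either way. If inclisiran produces more improvement and less worsening, the two effects pull the pooled event in opposite directions, and the odds ratio reflects whichever is numerically larger.

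The second problem is the name of the score. Protocol 8.5.1.1 describes two main SF-BPI scores, severity and interference, and uses intensity for the four items averaged into severity. The interference responder, a listed secondary endpoint, therefore has no threshold of its own in the visible text.

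If direction is settled only after the treatment codes are known, the choice between improvement and worsening can be driven by the data.

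**Working it through.** **Nothing to reproduce.** The documents give no rate, power or sample size for these endpoints. All rates and standard deviations below are assumptions. The only input from the plan is n = 880 per arm (Protocol 12.8.1, SAP 3.1).

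**Step 1: the texts side by side.** The definition and the analysis sentence in SAP 2.6.2.4 both lack a direction. Every listing of the endpoints (Protocol Table 2-1, 2.2 and 12.5; SAP Table 1-1, 1.2.2 and Table 2-3) speaks only of change. SAP section 4, on departures from the protocol, does not address it. No visible text supplies a sign.

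**Step 2: odds ratios under assumed rates.** With p1 the inclisiran and p0 the placebo proportion,

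OR = [p1/(1−p1)] / [p0/(1−p0)]

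95% CI = exp{ln OR ± 1.96 × √[1/(n·p1) + 1/(n(1−p1)) + 1/(n·p0) + 1/(n(1−p0))]}, unadjusted.

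The undirected proportion is the sum of improvers and worseners.

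| Inclisiran improve / worsen | Placebo improve / worsen | OR improvement | OR worsening | Undirected event | Undirected OR (95% CI) |
|---|---|---|---|---|---|
| 12% / 10% | 12% / 20% | 1.00 | 0.44 | 22% vs 32% | 0.60 (0.48–0.74) |
| 15% / 5% | 10% / 15% | 1.59 | 0.30 | 20% vs 25% | 0.75 (0.60–0.94) |
| 15% / 10% | 10% / 15% | 1.59 | 0.63 | 25% vs 25% | 1.00 (0.81–1.24) |
| 15% / 8% | 10% / 8% | 1.59 | 1.00 | 23% vs 18% | 1.36 (1.08–1.72) |

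Second row in full: OR = (0.20/0.80)/(0.25/0.75) = 0.75. SE = √(1/176 + 1/704 + 1/220 + 1/660) = 0.115. CI = exp(−0.288 ± 0.225) = 0.60 to 0.94.

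Inclisiran is better in at least one direction and worse in neither in every row, yet the undirected OR falls on both sides of 1. In three of the four rows its interval excludes 1.

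**Step 3: a continuous model.** Let the change be normal with mean μ and standard deviation σ, so that P(improve) = Φ((−2−μ)/σ) and P(worsen) = 1−Φ((2−μ)/σ). Fix a 0.5-point mean benefit and take σ = 1.5, 2.0 and 2.5. Across all cases the improvement OR is 1.41–2.00 and the worsening OR is 0.50–0.71. The undirected OR depends on where the two means lie:

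- inclisiran −0.5, placebo 0: 1.04 to 1.17
- inclisiran −0.25, placebo +0.25: 1.00
- inclisiran 0, placebo +0.5: 0.86 to 0.96

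The same treatment benefit moves from one side of 1 to the other with the common drift of both arms.

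**Step 4: floor of the scale.** On the 0–10 range, a participant with a baseline below 2 cannot fall by 2 points and can meet the undirected rule only by worsening. The documents give no baseline distribution, so the share of such participants is unknown.

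**The case against.** The best defence is that context supplies the direction. Higher scores are said to be worse, the objective is superiority, and the analysis sentence speaks of *achieving* the change, the verb used for reaching the LDL-C target. On that view improvement is meant and intensity is a slip for interference. The slip is very likely. The direction is less clear, because the design rationale also supports avoided deterioration. The protocol summary expects less intense lipid-lowering therapy with inclisiran, and Protocol 1.1 says statin-associated muscle symptoms are more frequent at higher doses. The two readings put benefit on opposite sides of 1.

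A second defence is that the responder analysis is only an addition to the MMRM and sits outside H01–H06. That stands and limits the consequence.

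Blacked-out SAP sections (2.6.6.2–2.6.6.4, 2.9.6–2.9.7) may hold further responder rules. That also stands, but the rule for these two endpoints is visible.

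Several stronger readings are tempting and are not supported:

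- *The odds ratio cannot show any effect.* It equals 1.00 only when the pooled rates match, as with mirrored rates. Otherwise it can differ from 1. What it lacks is a meaning as benefit or harm.
- *A responder must meet both conditions jointly.* The wording allows this, but Table 2-3 lists two separate endpoints, each with its own odds ratio.
- *Participants with a zero baseline drop out of H05 and H06, because SAP 2.1.1.6 computes relative change only for non-zero baselines.* The MMRM text specifies absolute change, Protocol 12.5.2.4 specifies mean change from baseline, and the endpoint column of Table 2-3 reserves relative change for LDL-C. The label looks copied.
- *The 1–10 range distorts the scores.* The scores are averages of items rated 0–10, and no visible derivation uses the stated range.

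**Conclusion.** The point holds for the two responder endpoints. As written, the rule pools improvement with worsening and gives interference no threshold, so the planned odds ratio, interval and p-value have no interpretable direction. Under assumed rates with no disadvantage for inclisiran in either direction, the undirected OR ranged from 0.60 to 1.36. These figures show that the sign of the result is uninformative; they do not predict the trial's result.

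A reader might infer that the confirmatory pain results are compromised. They are not: H05 and H06 are mean changes tested by an MMRM contrast at Day 360, and the responder endpoints are outside the testing hierarchy in SAP 2.6.2.5 and Protocol 12.5.1. The Table 2-3 label and the 1–10 range are editorial.

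**What to change.** Before unblinding, amend SAP 2.6.2.4 as follows:

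1. For severity and interference separately, define improvement as a change of −2 or lower and worsening as a change of +2 or higher.
2. State which of the two is the endpoint and which side of OR = 1 favours inclisiran. Report the other direction as supportive if wanted.
3. Replace intensity by interference in the definition and in the analysis sentence.

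As editorial alignment, change the SF-BPI summary measure in Table 2-3 to the difference in mean absolute change, matching the MMRM, and correct the score range to 0–10, matching Protocol 8.5.1.1.

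The cost is SAP wording and at most one extra logistic model per score. No new data are needed.

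### The two SF-BPI responder models omit the baseline SF-BPI score, although baseline limits who can change by 2 points; the power at stake depends on assumptions and on an unstated direction of change

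*SAP*

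**What the plan says.** SAP Table 2-3 lists two SF-BPI responder endpoints, for pain severity and pain interference, each summarised by an odds ratio. SAP 2.6.2.4 analyses them as follows: the odds ratio for a "clinically relevant change in pain severity score and pain intensity score from baseline to Day 360 will be estimated using a logistic regression model". On covariates it says: "Treatment and CV risk category will be included as factors in the model". Nothing else enters the model. The protocol lists both endpoints (2.2 and 12.5) but gives no model for them.

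The mixed models for mean change in the same two scores, in the same SAP section, include "corresponding baseline SF-BPI score and the interaction of corresponding baseline SF-BPI score with scheduled visit as covariates".

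Three features of the responder definition are unsettled:

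- **Direction.** A change is clinically relevant if the "pain severity score and the pain intensity score change by at least 2 points". Neither improvement nor worsening is named.
- **Score name.** SAP 2.6.2.4 pairs severity with intensity, where Table 2-3 pairs it with interference.
- **Range.** The SAP says "Both scores will be between 1 and 10"; Protocol 8.5.1.1 says "Both scores will be between 0 and 10".

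On error control, SAP 2.6.2.5 says "1-sided p-values and alpha level of 0.025 are considered for the testing procedure" and "The third family contains the remaining secondary hypotheses", namely H04 to H06: pain days and the two mean changes. The responder endpoints carry no hypothesis, and neither document plans power for them.

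**The concern.** A 2-point change on a bounded scale depends on where the participant starts. Someone near the bottom cannot improve by 2 points, and someone near the top cannot worsen by 2. Eligibility does not require pain, and myopathy is an exclusion (Protocol 5.1 and 5.2), so many low baseline scores are plausible, although neither document gives a distribution.

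Randomization is stratified by CV risk only (Protocol 6.4.2). A chance imbalance in baseline pain therefore goes uncorrected in this odds ratio, while the mixed models for the same scores correct for it. The SAP's general analysis of covariance for change from baseline (5.5.2.4) also adjusts for baseline. The responder models depart from that practice without a stated reason.

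What is at stake is the power of two supportive secondary comparisons and their protection against chance imbalance in pain.

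**Working it through.** **1. Is there a plan figure to reproduce?** No. The documents state no responder rate, effect, SD, baseline distribution, correlation or power for these endpoints. The inputs they do give are about 880 per arm (SAP 3.1), 1:1 allocation, the 2-point rule and the two score ranges.

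**2. The bound.** Improvement needs baseline − 2 ≥ scale minimum; worsening needs baseline + 2 ≤ scale maximum.

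- Range 0–10: no improvement is possible below 0 + 2 = 2, and no worsening above 10 − 2 = 8.
- Range 1–10: no improvement is possible below 1 + 2 = 3, and no worsening above 8.

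So the group that cannot improve depends on which range is right.

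**3. The models compared.**

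- Plan: logit(responder) = treatment + CV risk category
- Alternative: logit(responder) = treatment + CV risk category + baseline score (linear)

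**4. Simulation, with all distributional inputs assumed.** There were 880 per arm, scores limited to 0–10 in steps of 0.25, residual SD 1.6 and 80% very high risk. Four baseline distributions were used: 60% zeros, 40% zeros, skewed with mean about 2, and normal with mean about 4 and SD 2. The slope of Day 360 on baseline was 0.2, 0.4, 0.6 or 0.8. Effects were set to give unadjusted power near 50% or 80%, which makes 4 × 4 × 2 = 32 scenarios per direction. Each used 1,500 replicates and a Wald test at one-sided 0.025. The Monte Carlo SE of one power near 50% is √(0.5 × 0.5 / 1500) = 0.013.

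Selected results (gains taken before rounding):

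| Response | Baseline | Slope | Response rates, placebo / inclisiran | Power without | Power with | Gain (points) |
|---|---|---|---|---|---|---|
| Improve | 60% zeros | 0.2 | 15.4% / 18.9% | 50.7% | 91.3% | +40.6 |
| Improve | mean about 2 | 0.6 | 10.0% / 12.9% | 47.8% | 60.8% | +13.0 |
| Improve | mean about 4 | 0.8 | 11.9% / 16.7% | 81.7% | 83.1% | +1.3 |
| Worsen | mean about 4 | 0.2 | 20.3% / 16.7% | 51.6% | 65.4% | +13.8 |
| Worsen | 60% zeros | 0.4 | 17.3% / 12.4% | 82.6% | 84.7% | +2.1 |
| Worsen | 60% zeros | 0.6 | 14.7% / 10.1% | 83.3% | 82.9% | −0.4 |

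Across all scenarios:

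- Improvement: +1.3 to +40.6 points, median +13.7.
- Worsening: −0.4 to +13.8 points, median +2.7.
- Either direction: −0.7 to +1.2 points. This rests on 16 scenarios with 400 replicates, where effects were not calibrated and unadjusted power was only 2–17%. The near-zero gain is still expected: when response can occur at both ends of the scale, a linear baseline term carries little information.

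**5. Validity.** In four null scenarios the one-sided error was 0.023–0.030 without baseline and 0.022–0.033 with it. Omitting baseline does not invalidate the test. The highest value, 0.033, belongs to the adjusted model with 60% zeros.

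**6. Where the gain comes from.** In separate runs (slope 0.6, residual SD 1.5, improvement) the treatment log-odds ratio and its SE moved as follows:

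- Log-odds ratio 0.365 to 0.484, SE 0.152 to 0.177; the ratio goes from 0.365/0.152 = 2.40 to 0.484/0.177 = 2.73.
- Log-odds ratio 0.325 to 0.480, SE 0.162 to 0.199; the ratio goes from 0.325/0.162 = 2.01 to 0.480/0.199 = 2.41.

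The SE rises. Power rises because the conditional log-odds ratio moves further from zero than the SE grows.

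**The case against.** The case for leaving the model alone is reasonable. Treatment plus CV risk category is the specification of the primary and muscle-AE logistic models (SAP 2.5.2 and 2.6.2.2), and it is consistent and valid. Chance imbalance with about 880 per arm is already reflected in the confidence interval. The confirmatory SF-BPI tests, H05 and H06, do adjust for baseline. Adding baseline also changes which odds ratio is estimated. All of this stands, and it limits the point to an optional improvement.

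A further objection is that a linear term does not match a threshold constraint. For a one-directional responder the linear term still captured the gains shown above. For an either-direction responder it would not, which is why direction must be settled first. The SAP speaks of participants achieving a change, which suggests improvement. Worsening is also natural, because the protocol links higher statin doses to more muscle symptoms (1.1) and expects less intense background therapy on inclisiran (protocol summary).

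Three stronger readings are tempting, and the documents do not support them:

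- **A fixed power loss.** A reader might infer a band such as 7 to 23 points. One narrow set of improvement-only assumptions gives that (for example 19% to 26%, and 44% to 67%). A repeat of a similar setup gave +7 to +13 for improvement, +2 to +5 for worsening and about 0 for either direction. Every driving input is absent from the plan.
- **A more precise odds ratio.** Adjustment widens the interval on the log-odds scale (step 6).
- **A threat to the confirmatory conclusions.** These endpoints are outside H01 to H06.

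**Conclusion.** The point holds as a minor improvement. Both responder models omit a baseline score that is already collected, that limits who can respond, and that the companion models use. Adjustment would usually raise power and would remove the effect of chance baseline imbalance in pain. The size is not determined by the documents: about +1 to +41 points for improvement, about 0 to +14 for worsening, and about 0 for either direction. All of this assumes the baseline distributions, slopes, residual SD and effects listed above. The worst change seen in any scenario was −0.7 points, so there is essentially no power cost. The planned analysis remains valid and no alpha-controlled claim depends on it.

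**What to change.** In SAP 2.6.2.4:

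1. State whether the 2-point change is an improvement or a worsening.
2. Reconcile intensity with interference, and the 1–10 range with the protocol's 0–10.
3. Add the corresponding baseline SF-BPI score as a continuous covariate to each responder model: logit(responder) = treatment + CV risk category + baseline score.
4. Keep the crude proportions by arm as the descriptive display, and say that the odds ratio is conditional on baseline.

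The cost is one covariate in two models. No new data are needed: SF-BPI is scheduled at screening and Day 1 (Protocol Table 8-1). No participant is lost, because a change score already requires a baseline value. The small downside is that the odds ratio differs numerically from the one now planned and has a larger standard error on the log-odds scale. SAP section 1 places analysis decisions before database lock; if lock has passed, report the adjusted model as a labelled supplementary analysis beside the planned one.
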